### **3.2 Study Centers**

The study is planned at 5 study centers.

### **3.3 Number of Subjects**

Approximately 12 to 24 subjects (3 to 6 subjects in each cohort) will be enrolled in the study.

If any significant protocol deviation that affects DLT assessment is observed or a subject could not complete the protocol-specified MLN9708 treatment during the DLT-assessment period for reasons other than DLTs, the subject will be excluded from the DLT assessment, and additional subject(s) may be enrolled. Moreover, if there seems to be needs for additional data for safety or pharmacokinetics evaluation, the sponsor may decide to enroll additional subjects. See “[10.2 Sample Size Considerations](#) for the sample size justification.

### **3.4 Estimated Study Duration**

The study will be conducted between March 2012 and March 2019.

#### **3.4.1 Study Duration for Participants**

Study duration for patients will last for up to approximately 14 months, including maximum of 4 weeks screening period, maximum 12 cycles of treatment period (approximately 12 months), and 4 weeks follow-up after the last dose. Subjects may remain on treatment after the 12 cycles if the investigator and the sponsor determine that the subjects would derive benefit from continued therapy beyond 12 months.

### **3.5 Study Committees**

#### **3.5.1 ESEC**

An ESEC will be formed before starting the study and will be composed of 3 medical experts/oncologists who are not the investigators or the sponsor staff of this study.

The ESEC may evaluate the safety of MLN9708 and the appropriateness to continue this study upon the sponsor's request. Further details will be provided in the ESEC charter.

## **4. SUBJECT ELIGIBILITY**

Investigators must ensure that subjects meet all the eligibility criteria (inclusion criteria/exclusion criteria).

### **4.1 Inclusion Criteria**

Patients must give written consent to the participation and meet ALL of the following inclusion criteria to be eligible for the study.

#### **[Disease Related]**

- 1) Japanese patients with multiple myeloma according to diagnostic criteria shown in [Appendix E](#)
- 2) Previously treated with 2 or more regimens including all the following drugs
  - bortezomib
  - thalidomide or lenalidomide
  - corticosteroids
- 3) Patients who have relapsed following the previous therapy or failed to continue the treatment due to their intolerability to the last treatment regimen for myeloma
- 4) Measurable disease defined by at least one of the following 3 measurements
  - Serum M-protein:  $\geq 1$  g/dL ( $\geq 10$  g/L)
  - Urine M-protein:  $\geq 200$  mg/24 hours
  - Serum free light chain (FLC) assay: involved FLC level  $\geq 10$  mg/dL ( $\geq 100$  mg/L), provided that the serum FLC ratio is abnormal.
- 5) Eastern Cooperative Oncology Group (ECOG) performance status of 0 to 2

#### **[Demographic]**

- 6) Patients 20 years or older at giving their informed consent
- 7) Patients must be able to stay in the hospital for Cycle 1 treatment

#### **[Laboratory Values]**

Patients must meet the following laboratory criteria at screening. Patients must not receive granulocyte colony stimulating factor (G-CSF) or blood transfusion within 7 days before the test of neutrophil and platelet counts:

- 8) Absolute neutrophil count (ANC):  $\geq 1,000/\text{mm}^3$ 
- 9) Platelet count:  $\geq 75,000/\text{mm}^3$ 
- 10) Total bilirubin:  $\leq 1.5 \times$  the upper limit of normal range (ULN)
- 11) Alanine aminotransferase (ALT) and aspartate aminotransferase (AST):  
 $\leq 3 \times$  ULN
- 12) Creatinine clearance: calculated by using Cockcroft-Gault formula ([Appendix F](#))  
MLN9708 monotherapy cohort:  $\geq 30$  mL/min  
MLN9708 with Rd cohort:  $\geq 60$  mL/min

**[General]**

- 13) Patients recovered (Grade 1) from the toxicities of the prior treatments.  
ANC  $\geq 1,000/\text{mm}^3$ .
- 14) Life expectancy of at least 3 months, in the judgment of the investigator
- 15) Patients conforming to proper management guidelines of lenalidomide  
(MLN9708 with Rd cohort only).

<Basis for setting the criteria>

- (1) To enroll subjects who represent the intended indication population.
- (2) To minimize risks and ensure safety of subjects.

**4.2 Exclusion Criteria**

Patients meeting ANY of the following exclusion criteria cannot be enrolled in the study.

**[Disease related]**

- 1) Patients with plasmacytoma only
- 2) Patients with plasma cell leukemia
- 3) Patients with central nervous system invasion

**[Medications]**

- 4) Radiotherapy within 14 days before enrollment
- 5) Other anti-tumor drug administration within 21 days before enrollment
- 6) Other investigational products administration within 21 days before enrollment  
(60 days from the last dose for carfilzomib)
- 7) Antibody treatment within 42 days before enrollment

- 8) Systemic treatment with potent CYP1A2 inhibitors (fluvoxamine, enoxacin), potent CYP3A inhibitors (clarithromycin, telithromycin, itraconazole, voriconazole, ketoconazole), or potent CYP3A inducers (rifampin, rifabutin, carbamazepine, phenytoin, phenobarbital), or use of foods containing Ginkgo biloba extract, St. John's Wort, or grapefruit within 14 days before enrollment
- 9) Treatment with corticosteroids greater than 10 mg of prednisolone per day. Inhaled and topical steroids are permitted

**[Other Medical Conditions]**

- 10) Peripheral neuropathy  $\geq$  Grade 2
- 11) Diarrhea  $\geq$  Grade 2
- 12) Major surgery requiring general anesthesia within 14 days before enrollment
- 13) Infection requiring systemic antibiotic treatment or other serious infections within 14 days before enrollment
- 14) Evidence of concurrent uncontrolled cardiovascular conditions including hypertension, cardiac arrhythmias, New York Heart Association (NYHA) Class III or worse congestive heart failure, angina, myocardial infarction, or cerebral infarction within 6 months before enrollment
- 15) QTc > 470 milliseconds on a 12-lead ECG obtained during the screening period
- 16) Tested positive for human immunodeficiency virus (HIV) antibody, hepatitis B virus surface antigen (HBs antigen), or hepatitis C virus (HCV) antibody during the screening period
- 17) Hypersensitivity to MLN9708 (including excipients), boron, or boron-containing drugs
- 18) Hypersensitivity to lenalidomide, or dexamethasone, or excipients contained in the formulation of each drug (MLN9708 with Rd cohort only)
- 19) Known gastrointestinal diseases (difficulty swallowing, inflamed gastroenteritis, and Crohn disease), or gastrointestinal procedure (endoscopic procedure is permitted), that could interfere with the oral absorption or tolerance of the study treatment
- 20) Uncontrolled diabetes mellitus
- 21) A history of interstitial lung disease or lung fibrosis, or a current complication of interstitial lung disease or lung fibrosis diagnosed by chest imaging.
- 22) Prior or current complications of deep vein thrombosis or pulmonary embolism (MLN9708 with Rd cohort only)
- 23) Diagnosed or treated for another malignancy within 2 years before the first dose of MLN9708 or previously diagnosed with another malignancy and have any evidence of residual disease. Patients with nonmelanoma skin cancer or carcinoma in situ of any type are not excluded if they have complete resection

**[General]**

- 24) Patients who do not consent to use adequate contraceptive precautions (e.g. condoms and oral contraceptives) during the following term:
- For women with childbearing potential\*, from when giving their consent through 3 months after the last dose of MLN9708, dexamethasone, or lenalidomide
  - For men having their partners with childbearing potential, from when giving their consent through 4 months after the last dose of MLN9708, dexamethasone, or lenalidomide
- \* Women with child-bearing potential are those who are premenopausal (menopause is defined as the time when there has been no menstrual periods for at least 1 year), or who have not had a bilateral tubal ligation, bilateral oophorectomy, or hysterectomy. The menstruation possibly interrupted by chemotherapy is not defined as menopause.
- 25) Pregnant (e.g. positive for pregnancy test) or lactating. Lactation is prohibited from the first dose through 6 weeks after the last dose of MLN9708, dexamethasone, and lenalidomide
- 26) Use of an investigational medical device within 28 days before enrollment
- 27) Any inabilities that could potentially interfere with the consent or completion of treatment according to this protocol
- 28) Having difficulties in participation to this study by the investigator's judgment

<Basis for setting the criteria>

- (1) To minimize risks and ensure safety of subjects.
- (2) To eliminate any impact on evaluation of MLN9708.
- (3) For unclear potential of reproductive and developmental toxicity associated with MLN9708 and teratogenicity evident by lenalidomide in the Rd cohort.

## **5. SUBJECT ENROLLMENT**

The investigators must obtain written informed consent from all subjects before any study specific procedures are performed.

All subjects who enter into the screening period for the study (defined as the point at which the subject signs the informed consent) will receive a unique, 8-digits subject identification number (e.g. 34XXXYYY). The first 2 digits (i.e. 34) represent the protocol number, next 3 digits (XXX) represent the study center number, and the last 3 digits (YYY) represent the subject number which is assigned in each study center.

This number will be used to identify the subject throughout the study and must be used on all study documentation related to that subject. The subject identification number must remain the same throughout the entire clinical study; it must not be changed at the time of re-screening or re-enrollment. The number is assigned in sequential order of the subject's consent at the site, in principle (e.g. 001, 002, 003).

Subjects must be registered within 28 days of the consent.

Subjects not meeting the eligibility criteria during the screening period cannot be enrolled. However, subjects can be re-screened with the investigator's discretion as long as they are not registered as a screen failure. When subjects are re-screened, the investigators must obtain additional written informed consent before the re-screening to reconfirm the subject's consent for study participation. A subject cannot be re-screened more than once, and will be defined as a screen failure if subject is not qualified to undergo re-screening or is determined as a screen failure after the re-screening.

A subject will be defined as a screen failure, if the subject signs the informed consent but fails to enroll into the study. The investigators must document all screen failures and the reasons for the failure on the electronic case report form (eCRF).

For addition or replacement of subjects, refer to "[8.2 Replacement of Subjects](#)".

## **5.1 Enrollment Procedures**

After the completion of subject screening for each subject, the investigator enrolls the subject according to the following procedures:

The investigator ensures that a subject meets all the eligibility criteria and faxes a “subject registration sheet” to the Registration Center after confirming the necessary information is completed. The “subject registration sheet” may be the source data of the investigator’s judgment for the each eligibility criteria.

The Registration Center confirms that a subject meets the all inclusion criteria and does not meet any of the exclusion criteria, and then the Registration Center identifies the subject as an enrolled subject and faxes a “registration confirmation sheet” to the investigator. If a subject is considered ineligible by the Registration Center, the center will not identify the subject as an enrolled subject. A “registration confirmation sheet” describing the “reason for ineligibility” will be faxed to the investigator.

The investigator must retain a “subject registration sheet”, a “registration confirmation sheet”, and the “reason for ineligibility” as the source documents appropriately in the study centers.

The Registration Center will report above subject registration progress promptly to the sponsor.

MLN9708 (TB-MC010034) Subject Registration Center Takeda Pharmaceutical Company Limited [name] PPD PPD PPD
---

## **5.2 CCI Registration**

The CCI procedures must be followed when providing lenalidomide to the subjects in the MLN9708 with Rd cohort in the study.

Before a patient is enrolled in this study, the patient must be registered in accordance with the CCI [REDACTED], and it must be confirmed that the patient is eligible to receive lenalidomide.

If the patient is already registered in CCI [REDACTED], then no re-registration is necessary.

## 6. TREATMENT PROCEDURES

### 6.1 MLN9708

MLN9708 is manufactured (including packaging and labeling) by MPI and supplied by Takeda Pharmaceutical Company.

Specifications and storage conditions for MLN9708 are presented below.

**Table 6-1. Specifications for MLN9708**

Investigational Product	MLN9708
Formulation and strength	capsules One capsule contains 2.3, 3.0, 4.0, or 5.5 mg of active boronic acid form of MLN9708 (MLN2238)
Packaging	foil-foil blisters
Packaging Unit	Three capsules per foil-foil blister, which is contained by 1 unit carton.
Storage	to be refrigerated at 2°C to 8°C
Manufacturer	Millennium Pharmaceuticals, Inc. (the United States)

See the Directions for Use located in the Pharmacy Manual for details on the labeling and storage of MLN9708. There is very limited experience with clinically significant overdose of MLN9708 and no specific antidotes exist for the treatment of MLN9708 overdose. General supportive care is recommended.

The maximum dose of MLN9708 previously used in monotherapy was 3.95 mg/m^2 weekly.

### 6.2 Concomitant medications

The concomitant medications (MLN9708 + Rd cohort only) are described below. The concomitant medications will be dispensed at the study center.

#### 6.2.1 Lenalidomide (CCI [REDACTED] 5 mg)

Lenalidomide (CCI [REDACTED] 5 mg) is an anti-angiogenic malignant tumor agent that is indicated for relapsed and/or refractory multiple myeloma and myelodysplastic

syndromes with 5q- syndrome. For detailed information about lenalidomide, refer to the latest version of the package insert for [REDACTED] 5 mg.

### **6.2.2 Dexamethasone ([REDACTED] 4 mg)**

Dexamethasone ([REDACTED] 4 mg) is a corticosteroid that is indicated for multiple myeloma. For detailed information on dexamethasone, refer to the latest version of the package insert for [REDACTED] 4 mg.

## **6.3 Dosage, administration method, dosing schedule**

### **6.3.1 MLN9708 administration**

In this study, MLN9708 will be administered orally once weekly for 3 weeks (on Days 1, 8, and 15 and skip Day 22) in a 28-day cycle for up to 12 cycles.

MLN9708 will be taken on an empty stomach at least 1 hour before or no sooner than 2 hours after a meal.

In Cycle 1, MLN9708 will be given according to the dosage and administration specified in this study protocol; no interruption, delays, or reduction will be permitted.

Missed doses of MLN9708 in Cycle 2 and subsequent cycles can be taken as soon as the patient remembers provided that at least 3 days elapses between doses (until Day 4). If a patient vomits after taking MLN9708, the patient should not repeat the dose, but resume dosing at the time of the next schedule.

Once a dose is reduced, no re-escalation will be permitted.

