## 6.5 Dose Modification

### 6.5.1 MLN9708 Monotherapy

#### 6.5.1.1 Criteria for Dose Modification

Dose modifications of MLN9708 are not permitted in Cycle 1.

If dose modification is required in Cycle 2 or subsequent cycles, MLN9708 dose will be reduced by one level according to [Table 6-2](#). If multiple toxicities are noted, the dose should be interrupted or reduced according to the most severe toxicity guidelines ([Table 6-3](#) and [Table 6-4](#)). Toxicity will be assessed according to the Common Terminology Criteria for Adverse Events (CTCAE) version 4.03.

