#### 6.5.1.1.1 Dose Modification for Hematological Toxicity

If platelet count is less than 30,000/mm^3 or ANC is less than 750/mm^3 in Cycle 2 or subsequent cycles, MLN9708 dose should be interrupted. If the platelet count is recovered to at least 30,000/mm^3 and ANC is recovered to at least 750/mm^3 within the same cycle, MLN9708 may be reinitiated with one dose level reduction. If the subject meets the criteria for retreatment by delaying the initiation of the subsequent cycle, the subjects may be retreated with MLN9708 with one dose level reduction (See “[6.4 Criteria for Beginning the Next Cycle of Treatment](#)”).

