## 6.5.2 MLN9708 in combination with Rd

### 6.5.2.1 Criteria for Dose Modification

Dose modifications of MLN9708 are not permitted in Cycle 1. Dose modifications of Rd should be avoided as much as possible. If a subject experiences an adverse event(s) considered strongly related to lenalidomide or dexamethasone and the investigator considers it difficult to continue the treatment with Rd, the investigator and the sponsor will discuss the alternative dose modification.

If dose modification is required in Cycle 2 or subsequent cycles, MLN9708, lenalidomide, or dexamethasone dose will be modified levels according to [Table 6-5](#). If multiple toxicities are noted, the dose should be modified or delayed according to the most severe toxicity guidelines ([Table 6-6](#) through [Table 6-11](#)). Once a dose is reduced, no re-escalation will be permitted.

Each adverse event should be attributed to a specific drug, if possible, so that the dose can be modified accordingly. Reduction of one agent and not the other is appropriate if toxicity is related primarily to one of the agents. Toxicity will be assessed according to the CTCAE version 4.03.

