## **6.7 DLT**

### **6.7.1 DLT Assessment Period**

DLTs will be assessed from the first dose until Cycle 2 Day 1 of MLN9708 treatment.

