### **6.7.2 DLT-Evaluable Subjects**

DLT-evaluable subjects are defined as follows:

- DLTs  $\geq 1$  during DLT-assessment period.

OR

- Received 3 doses of MLN9708 specified for the applicable cohort and completed the DLT-assessment period.

Subjects whose treatment with MLN9708 was interrupted or reduced in Cycle 1 for reasons other than DLTs are not eligible for DLT assessment in principle.

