### **6.7.3 Definitions of DLT**

DLT will be defined as any of the following AEs that are considered possibly related to MLN9708. Toxicity will be assessed according to the CTCAE version 4.03.

1. Grade 4 neutropenia ( $ANC < 500/mm^3$ ) lasting more than 7 consecutive days.
2. Grade 3 or greater neutropenia ( $ANC < 1,000/mm^3$ ) with fever and/or infection, where fever is defined as axillary temperature  $\geq 38.0^\circ C$ .
3. Grade 4 thrombocytopenia (platelets  $< 25,000/mm^3$ ) lasting more than 7 consecutive days.
4. Grade 3 or greater thrombocytopenia ( $< 50,000/mm^3$ ) with clinically significant bleeding, or which requires blood transfusion.

5. A platelet count < 10,000/mm^3.
6. Grade 2 peripheral neuropathy with pain or Grade 3 or greater peripheral neuropathy.
7. Any other Grade 3 or greater nonhematologic toxicities with the following exceptions:
  - Grade 3 or greater arthralgia/myalgia.
  - Grade 3 or greater fatigue lasting less than 7 days.
  - Grade 3 nausea and/or emesis which can be controlled with anti-emetic therapies including anti-emetic prophylaxis. Anti-emetic prophylaxis is defined as an anti-emetic regimen that employs a 5-HT3 antagonist given in standard doses and according to standard schedules. Dexamethasone should not be administered as an anti-emetic.
  - Diarrhea that is controlled with appropriate supportive care
8. A delay of more than 14 days in the initiation of Cycle 2 treatment because of a lack of adequate recovery of MLN9708 related hematological or nonhematologic toxicities.
9. Other Grade 2 or greater MLN9708 related nonhematologic toxicities that, in the opinion of the investigator, require permanent discontinuation of MLN9708.
10. Inability to give at least 80% of the planned lenalidomide doses (Rd combination cohort only) due to the adverse events related to MLN9708.

When a subject experiences any of the above DLTs, MLN9708 therapy should be interrupted within the same cycle after DLT. With agreement by the sponsor, investigators may consider restarting the MLN9708 therapy from next cycle for subjects continue to clinically benefit from the therapy. MLN9708 should be reinitiated in accordance with “[6.4.3 Criteria for Dose Delays](#)”.

The sponsor will consult with the ESEC for the final decision if determination of DLT or subjects’ eligibility for DLT-assessment is difficult.

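### Sections 6.3.1 and 6.7.3 give opposite MLN9708 instructions when a DLT occurs before the Day 8 or Day 15 dose of Cycle 1

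*Protocol*

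**What the plan says.** Three protocol sections bar changes to MLN9708 in Cycle 1. Section 6.3.1, which applies to every cohort, says that "no interruption, delays, or reduction will be permitted". Section 6.5.1.1 (monotherapy) says "Dose modifications of MLN9708 are not permitted in Cycle 1". Section 6.5.2.1 (combination) repeats this and treats the partner drugs more loosely: "Dose modifications of MLN9708 are not permitted in Cycle 1. Dose modifications of Rd should be avoided as much as possible". None of the three mentions DLTs.

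The DLT sections read differently. Section 6.7.1 sets the window: "DLTs will be assessed from the first dose until Cycle 2 Day 1 of MLN9708 treatment". Section 6.7.3, after listing the ten DLT criteria, says that "MLN9708 therapy should be interrupted within the same cycle after DLT". It allows a restart to be considered from the next cycle, with the sponsor's agreement. Section 6.7.2 provides for subjects whose MLN9708 was "interrupted or reduced in Cycle 1 for reasons other than DLTs are not eligible for DLT assessment in principle". That sentence treats a DLT as an accepted reason to interrupt and foresees other reasons as well.

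**The concern.** The post-DLT instruction in section 6.7.3 operates within the DLT window, and that window is Cycle 1. This is the one cycle in which section 6.3.1 rules out interruption. An investigator whose subject has a DLT before the Day 8 or Day 15 dose therefore finds one section saying that the dose is not to be interrupted and another saying that it should be. No cross-reference or order of precedence settles which applies, and either action departs from one section as written.

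What is at stake is the safety of a subject who has just met a DLT criterion, in the first study of this drug in Japan. Section 6.7.2 adds a second uncertainty. It lays down what happens to DLT evaluability after an interruption for another reason, while section 6.3.1 says that no such interruption is permitted.

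**Working it through.** No sample size or power figure bears on this point. The check sets the sections side by side.

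**Step 1: which doses are in dispute.** MLN9708 is given on Days 1, 8 and 15 (section 6.3.1), so Cycle 1 has 3 doses. The doses left after a DLT are 3 minus the doses already given.

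| When the DLT is established | Cycle 1 doses left | Section 6.3.1 | Section 6.7.3 |
|---|---|---|---|
| After the Day 1 dose, before the Day 8 dose | 3 − 1 = 2 | no interruption | interrupt |
| After the Day 8 dose, before the Day 15 dose | 3 − 2 = 1 | no interruption | interrupt |
| After the Day 15 dose | 3 − 3 = 0 | nothing left to give | nothing left to withhold |

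The sections conflict in the first two rows only.

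**Step 2: which DLTs can fall in those rows.** Several criteria in section 6.7.3 can be met at once. Examples are platelets below 10,000/mm³, Grade 3 or greater thrombocytopenia with significant bleeding or transfusion, Grade 3 or greater neutropenia with fever or infection, and painful Grade 2 neuropathy. The two duration criteria need a Grade 4 count (platelets below 25,000/mm³ or ANC below 500/mm³) for more than 7 consecutive days. Scheduled Cycle 1 haematology is on Days 1, 8, 15 and 22 (section 7.2.2). A Grade 4 count first seen on Day 8 has lasted 15 − 8 = 7 days on Day 15, which is not more than 7. The next scheduled count is Day 22, after the last Cycle 1 dose. On scheduled counts, then, the conflict arises through the criteria that need no duration. An earlier onset found on an unscheduled count could add to these.

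**Step 3: does the choice of section change the DLT count?** Under section 6.7.2 and SAP section 7.2, one DLT in the window is enough to make a subject evaluable. Receiving all three doses is the alternative route, for subjects without a DLT. A subject with a DLT is therefore counted once, whether or not the remaining doses are given, and the cohort tally used in section 6.6.1 is unchanged.

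**Step 4: the monotherapy count thresholds.** From Cycle 2, platelets below 30,000/mm³ or ANC below 750/mm³ interrupt MLN9708. Section 6.5.1.1.1 writes the limit into the rule: "in Cycle 2 or subsequent cycles, MLN9708 dose should be interrupted". In Cycle 1, without fever, infection, significant bleeding or transfusion, platelets from 10,000 to below 30,000/mm³ or an ANC below 750/mm³ are not a DLT on a single count. The rules for Cycle 1 and for later cycles differ, but the difference is explicit. Table 6-3 itself labels its row as within-cycle modification on Days 8 and 15 and states no cycle. The Cycle 2 limit stands only in the text of sections 6.5.1.1 and 6.5.1.1.1.

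**The case against.** The best answer is that section 6.7.3 is the specific rule and section 6.3.1 the general one. Section 6.7.2 speaks of interruptions for reasons other than DLTs, so it assumes that a DLT is a legitimate reason. Section 6.3.1 also ties Cycle 1 dosing to what the protocol specifies, which could be read to include section 6.7.3. A sensible investigator may well reach that reading, and section 9.2 leaves removal from treatment for an adverse event to clinical judgment. This narrows the practical risk but does not remove the contradiction. The bar is written three times with no exception. Section 6.5.2.1 gives an investigator–sponsor discussion route for Rd in Cycle 1 but none for MLN9708. Sections 8.1 and 9.2 deal with removal from treatment or study, not with withholding a single dose.

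Two stronger readings are tempting, and the other side is right about both.

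- *A reader might infer that the bar contradicts the protocol's own count thresholds by making dosing mandatory at counts that interrupt MLN9708 from Cycle 2.* It does not, because sections 6.5.1.1 and 6.5.1.1.1 confine those thresholds to Cycle 2 onward. The difference also concerns monotherapy: in the Rd cohorts a first fall from Cycle 2 interrupts lenalidomide and MLN9708 can continue (sections 6.5.2.2.1 and 6.5.2.2.2). Platelets of 25,000 to 29,999/mm³ and ANC of 500 to 749/mm³ are not Grade 4, so no 7-day criterion applies to them. Mandatory is too strong a word given sections 6.7.2, 8.1 and 9.2.
- *A reader might infer that the tolerability result depends on which section a site follows, so that a cohort moves between 0/3 and 1/3.* Step 3 shows that it does not for a subject with a DLT. A hold for another reason makes the subject non-evaluable in principle, and additional subjects may be enrolled (sections 3.3, 6.7.2 and 8.2). The subject is not simply recounted as free of DLT among the same three.

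**Conclusion.** The contradiction stands. For a DLT established before the Day 8 or Day 15 dose, sections 6.3.1 and 6.7.3 give opposite instructions on one or two doses, in all four cohorts. Section 6.7.2 is also inconsistent with the unqualified bar. This is a safety-relevant inconsistency in the DLT period that should be corrected. It is not a flaw in how DLTs are counted.

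It affects only subjects with an early DLT, or those for whom an interruption for another reason is considered. The documents give no basis for estimating how many that would be, so counting every Day 8 and Day 15 dose as affected would overstate it. The conclusion rests on reading the sections as written, without an implied order of precedence.

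The position of Table 6-3 is a related point of clarity, not a second contradiction: a site using the table on its own could apply it in Cycle 1.

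**What to change.** Reconcile sections 6.3.1, 6.5.1.1 and 6.5.2.1 with sections 6.7.2 and 6.7.3. One statement should say whether, and for what reasons, MLN9708 may be interrupted in Cycle 1. The post-DLT instruction and the DLT-evaluability rule should then agree with that statement and refer to it. For the monotherapy cohorts, the statement should make clear that it governs Cycle 1 Days 8 and 15, and Table 6-3 should carry its own cycle limit. The clinical rule is for the sponsor to set, and no view on it is offered here.

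The cost is protocol wording only. No visits or tests are added, since haematology is already scheduled on Days 8 and 15 of Cycle 1, and the definition of the SAP's DLT analysis set need not change for subjects with a DLT.
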